5.0 Procedures Involved

5.1 Study Design:

This is a single center, single-blind randomized cross over design trial that will compare the impact of intranasal naloxone vs. intranasal saline administration during exercise on day 1 on the response to hypoglycemia on day 2.

Figure 1. Study Design

5.2 Study Procedures:

Screening Visit: At the screening visit, informed consent will be obtained; a standardized form will be used to insure participants meet inclusion/exclusion criteria, and baseline hemoglobin A1c will be collected. Clinical A1c from the medical record can be used if within one month of screening.

Following the collection of blood samples, participants will have their peak aerobic capacity (VO_2 peak) determined. Participants will be fitted with a neoprene breathing mask that is connected to an open-circuit spirometry metabolic cart for the collection of expired gas samples. After a warm-up on an electronically-braked bicycle ergometer for 5 minutes, participants will complete a progressive resistance exercise test until volitional exhaustion. VO_2 peak will be measured using methodology and equipment already established by our group (9). This measurement will then be used to determine the exercise workload necessary to achieve 60% of VO_2 peak during the intervention phases of the study, as was done by Milman (1).

-6 days Part 1 Day 1: In preparation for the intervention visits, participants will be instructed to avoid hypoglycemia in the week before day 1 since that may blunt their response to hypoglycemia during the protocol. They will be asked to avoid exercise, to wear a continuous glucose monitor (provided by the study) during the 6 days before the exercise study and the one day after, and to

PROTOCOL TITLE: Hypoglycemia after exercise in type 1 diabetes: Intranasal naloxone as a novel therapy to preserve hypoglycemia counterregulation

VERSION 8 – December 7, 2018

monitor and record their blood sugars before meals, at bedtime, and any time they have symptoms of hypoglycemia. Participants will also be given instructions for diabetes management during the days before the study to safely ensure at home insulin has cleared the body by the start of the study.

Participants will be instructed to call the investigators if they have symptomatic hypoglycemia with a glucose of <70 mg/dL or asymptomatic hypoglycemia with a glucose of <54 mg/dL during the 6 days before the exercise studies, after discharge on day 1 or before the hypoglycemic clamp is started on day 2. Participants will be rescheduled if they have episodes of hypoglycemia (defined as symptomatic hypoglycemia and a blood glucose or CGM reading <70 mg/dL or asymptomatic hypoglycemia with a blood glucose of < 54 mg/dL) for more than 20 minutes in the days before Day 1 of the study.

Part 1 Day 1: Participants will be instructed to report for the visit in a fasting state. Before any other research procedures take place, participants will be randomized to receive either naloxone or saline. Intravenous catheters will be placed for the subsequent infusion of 1.0 mU/kg/min insulin, potassium phosphate or potassium chloride (120 mEq/l at 40 cc/hr), and 20% dextrose as needed to maintain euglycemia. When participants reach euglycemia (~ 95 mg/dL), they will be instructed to begin exercise on a stationary bicycle. Adjustments in the exercise workload will be made to assure that participants exercise at a workload requiring 60% of their VO₂peak for 45 minutes based on the VO₂ measured every 15 minutes. They will then be given a 5 minute rest break, followed by another 45 minute period of exercise at 60% VO₂peak. At the start of exercise and 45 minutes after the start of the morning exercise period, participants will be given a 4.0 mg doses of intranasal naloxone or saline in the same volume, according to the randomization assignment.

Participants may be asked to allow a download of their personal glucose meter/pump data. This will be done in research offices using secure software specific for the brand of the glucose meter/pump.

At the completion of the morning exercise, participants will be allowed to rest 3 hours and eat a 15g carbohydrate measured snack. Glycemia will be maintained at euglycemia during this rest period.

At 1 pm, the afternoon period of exercise will start and will be maintained as in the morning for a total of 2 hours. A third dose of 4.0 mg intranasal naloxone or the same volume of saline will be administered at the start of the afternoon exercise, and a final dose of 4.0 mg intranasal naloxone will be given 45 minutes after the start of the afternoon exercise. Blood samples for subsequent measurement of naloxone will be collected at 4-5 predetermined time points from each participant to allow subsequent population pharmacokinetic modeling. After completing the afternoon exercise, participants will be sent home with instruction on avoiding hypoglycemia and using the CGM. Before participants are sent home, a meal will be provided.

Part 1 Day 2: Participants will return the following day, and undergo a two-hour hyperinsulinemic (infusion of 2.0 mU/kg/min) hypoglycemic clamp in which blood glucose will be allowed to drop to 50 mg/dL. Symptom scores will be collected using a standardized questionnaire before and every 15 minutes during the hypoglycemic clamp study. Samples for later measurement of epinephrine, norepinephrine, glucagon and cortisol will be collected at baseline and every 15 minutes during the two-hour infusion period. After completing the clamp, participants will be

PROTOCOL TITLE: Hypoglycemia after exercise in type 1 diabetes: Intranasal naloxone as a novel therapy to preserve hypoglycemia counterregulation

VERSION 8 – December 7, 2018

given a meal and instructions for using the CGM for the next 7 days. At the completion of Part 1, participants will be scheduled to return to complete part two to receive the alternate therapy.

Wash-out Period: For a total of approximately 7 weeks, participants will be instructed to continue with all normal activities.

Seven days before scheduled Part 2 Visit: Participants will be asked to come in for a visit to apply the CGM. Application of the sensor and instructions are as above.

Part 2 Day 1 and Part 2 Day 2: The second part of the study will follow exactly as above with the exception that the participant will receive the alternate therapy to complete the cross-over. Those who received naloxone in Part 1 will receive saline in Part 2, and vice versa.

A mid-point A1C may be collected at this visit. A clinical A1C from the medical record can be used if within three months of the Screening A1C.

5.3 Follow-Up:

Participants will be contacted at 1 week post final study procedure for adverse event assessment. This can be done by either telephone or email.

PROTOCOL TITLE: Hypoglycemia after exercise in type 1 diabetes: Intranasal naloxone as a novel therapy to preserve hypoglycemia counterregulation

VERSION 8 – December 7, 2018

	Screening	-6 to -1 days Part 1 Day 1	Part 1 Day 1		Part 1 Day 2	+1 to +7 days Part 1 Day 2	7 Week Washout Period	CGM-Only -7 Days before Part 2	-6 to -1 days Part 2 Day 1	Part 2 Day 1		Part 2 Day 2	+1 to +7 days Part 2 Day 2
			AM	PM						AM	PM		
Consent	X												
A1c	X										X		
VO ₂ peak/bike	X												
Education	X												
Urine Pregnancy Test	X		X								X		
Apply CGM	X								X				
Wear CGM		X	X	X	X	X				X	X	X	X
Home blood sugar monitoring		X				X				X			X
Randomization			X										
Download glucose meter/pump			X								X		
Exercise			X	X							X	X	
IV Infusion (insulin, glucose, potassium)			X	X	X						X	X	X
Naloxone/saline			X ¹	X ¹							X ¹	X ¹	
Blood collection: naloxone concentrations (only collected during active study drug)			X ²	X ²							X ²	X ²	
Blood collection: hormones (epinephrine, norepinephrine, glucagon, cortisol)					X ⁶								X ⁶
Glucose measurement			X ⁵	X ⁵	X ⁵						X ⁵	X ⁵	X ⁵
Blood Pressure	X												
Heart Rate			X ³	X ³							X ³	X ³	
VO ₂			X ⁴	X ⁴							X ⁴	X ⁴	
Questionnaires	X				X ⁷								X ⁷
Usual Activities							X						
Snack, if necessary			X	X	X						X	X	X
Meal				X	X						X	X	

¹ Naloxone/saline 4.0mg administered twice, time zero and +30 minutes

² Serum collection for naloxone at time points every 20-40 minutes

³ Heart rate collected continuously

⁴ VO₂ collected every 15 minutes

⁵ Collected from IV, resulted on bedside Analox machine

⁶ Serum collection: hormones

⁷ Questionnaires every 15 minutes

PROTOCOL TITLE: Hypoglycemia after exercise in type 1 diabetes: Intranasal naloxone as a novel therapy to preserve hypoglycemia counterregulation

VERSION 8 – December 7, 2018

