3.0 Study Endpoints/Events/Outcomes

3.1 Primary Endpoint/Event/Outcome:

The primary outcome variable for Aim 1 will be the difference, naloxone vs. saline, in symptom scores collected using a standard questionnaire during the hypoglycemic clamp on Day 2, after administration of intranasal treatment during exercise on Day 1.

The primary outcome variable for Aim 2 will be the difference, naloxone vs. saline, in peak epinephrine levels measured during the hypoglycemic clamp on Day 2, after administration of treatment during exercise on Day 1.

3.2 Secondary Endpoint(s)/Event(s)/Outcome(s):

Secondary endpoints will include:

- Glucose levels will be measured by continuous glucose monitor and home blood glucose monitoring during the 7 days after each experiment with specific levels of interest of > 54 mg/dL, > 54 mg/dL - < 70 mg/dL, and ≤ 70 mg/dL.
 - Percentage of time of specific ranges
 - Total count of specific ranges
 - Total hypoglycemia symptoms counted during specific ranges
- Plasma naloxone concentrations will be collected to model the pharmacokinetics and pharmacodynamics using a population modeling approach. This will be used to investigate dose levels and regimens for future studies.

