4.0 Study Intervention(s)/Investigational Agent(s)

4.1 Description:

This is a single center, single-blind randomized cross over design trial that will compare the impact of intranasal naloxone vs. intranasal saline administration during exercise on day 1 on the response to hypoglycemia on day 2.

Our investigational product is Narcan® intranasal spray, manufactured by ADAPT Pharma, which contains 4 mg naloxone in each metered dose. Naloxone is an opioid antagonist and is FDA approved as both intravenous and intranasal formulations for the complete or partial reversal of opioid depression, including respiratory depression, induced by natural and synthetic opioids.

4.2 Drug/Device Handling:

Investigational Drug Services will handle all drug requirements including randomization and blinding, dispensing, and storage.

4.3 IND/IDE:

[figure not shown]
Exempt IND #134687

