18.0 Provisions to Monitor the Data to Ensure the Safety of Participants

18.1 Data Integrity Monitoring.

While there will be no planned interim data analysis, the PI will periodically review data for completeness and to ensure that all procedures are being followed as detailed in the protocol. The assigned Regulatory Specialist or CTSI monitor will also perform periodic quality assurance monitoring at any point requested by the PI or at least annually.

18.2 Data Safety Monitoring.

An unblinded Data and Safety Monitoring Board (DSMB) will be assembled, including the following individuals:

- Independent monitor: endocrinologist with clinical and research experience.
 - [name]. Associate [name] of Pediatric Endocrinology. Department of Pediatrics, University of Minnesota
- Independent monitor: endocrinologist with clinical and research experience.
 - [name]. Associate Professor of Pediatric Endocrinology Department of Surgery, University of Minnesota
- Study monitor: statistician with research experience
 - [name]. Associate [name] of Biostatistics, School of Public Health, University of Minnesota

The DSMB will review any incidence of early stopping of the study and any incidence of an adverse or serious adverse event at time points of post-5, 10, 15 randomizations and at the final randomization. If at any point, during Part 1 or Part 2, the study was stopped early and an adverse or serious adverse event was reported, the DSMB will review that participant's

PROTOCOL TITLE: Hypoglycemia after exercise in type 1 diabetes: Intranasal naloxone as a novel therapy to preserve hypoglycemia counterregulation

VERSION 8 – December 7, 2018

data within two weeks. The DSMB will be informed of all adverse and serious adverse events within 48 hours and other events within 7 days. The DMSB may recommend termination of the study at any time based on safety concerns.

The Principal Investigator will oversee the safety of the study, including careful assessment and appropriate reporting of adverse events. All adverse and serious adverse events will be discussed with the PI within 48 hours for standard assessments (causality, expectedness, severity, and seriousness). IRB and other regulatory reporting requirements will be reviewed by study staff and followed with assistance of the Regulatory Specialist assigned to the study.

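### The protocol calls the trial single-blind without saying who is blinded, and nothing masks the staff who run the Day 2 clamp and collect symptom scores, or the PI who judges adverse-event causality

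*Combined protocol and SAP*

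**What the plan says.** Section 5.1 states: "This is a single center, single-blind randomized cross over design trial". Section 4.1 repeats the sentence, and the study summary does not mention blinding. Section 4.2 adds: "Investigational Drug Services will handle all drug requirements including randomization and blinding, dispensing, and storage". The blinded party is never named. The DSMB is the only group whose status is given; section 18.2 makes it unblinded.

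Matching is described by volume: "participants will be given a 4.0 mg doses of intranasal naloxone or saline in the same volume, according to the randomization assignment" (section 5.2). The active product is a branded metered spray (section 4.1), and nothing is said about the look or label of the saline device. In the schedule table after section 5.3, the row for naloxone concentrations carries the note "only collected during active study drug". Section 5.2 describes this sampling for each participant without that limit, and says Part 2 repeats Part 1 except for the therapy. On the crossover it says: "Those who received naloxone in Part 1 will receive saline in Part 2, and vice versa".

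The Aim 1 outcome is the treatment difference "in symptom scores collected using a standard questionnaire during the hypoglycemic clamp on Day 2" (section 3.1). Section 5.2 gives the timing: "Symptom scores will be collected using a standardized questionnaire before and every 15 minutes during the hypoglycemic clamp study". Aim 2 is peak epinephrine, from clamp samples assayed later. Section 14.1 lets the attending MD or PA stop a session on safety judgement, and section 18.2 has the PI assess the causality of every adverse event.

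**The concern.** In common use, single-blind means that participants are masked and study staff are not. On that reading, the people in the room on Day 2 may know what was sprayed on Day 1 while they collect a subjective primary outcome, control the glucose profile and may end the session. The PI may also know the treatment when judging causality. None of these tasks requires that knowledge.

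The crossover widens the exposure, because anyone who learns the treatment in one part knows it for the other. If drug-level blood is drawn only under naloxone, the sampling itself discloses the assignment to anyone who sees it or reads the Day 1 record, however well the spray is disguised.

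At stake is a shift in scores that follows treatment and so cannot be told apart from a drug effect.

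**Working it through.** **Who is masked, by task**

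| Task | Where | Masking stated? |
|---|---|---|
| Holding randomization, dispensing | 4.2 | Pharmacy service handles it |
| Giving the Day 1 spray | 5.2 | No; same volume only |
| Drawing naloxone samples | 5.2, schedule table | No; the schedule ties it to active drug |
| Running the Day 2 clamp | 5.2 | No |
| Collecting questionnaires | 5.2 | No |
| Stopping a session | 14.1, 18.2 | No |
| Judging causality | 18.2 | No |
| DSMB review | 18.2 | Unblinded |

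**The two sampling statements.** Every participant receives naloxone once, so sampling each participant and sampling only under active drug could both be true. But section 5.2 places the sampling in Part 1 without condition and has Part 2 follow the same procedures, which read literally means sampling in both periods. The schedule says otherwise. Only the schedule's rule reveals the treatment.

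**Inputs for the illustration.** SD of paired differences 12.9, target 7.53 points, 25 completers, 80% power (section 16.2); significance level 0.05 (section 16.1). Sidedness is not stated.

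**Reproducing the plan's figure**
- Standard error: 12.9/√25 = 2.58.
- Noncentrality at the target: 7.53/2.58 = 2.92.
- Two-sided paired t-test, 24 degrees of freedom: power 0.7996, so the plan's 80% reproduces. With 23 degrees of freedom, allowing for a period term, power is 0.798.
- Normal approximation: ((1.960 + 0.842) × 12.9/7.53)² = 23.04, so 24. A one-sided test gives 18.1, so 19. Two-sided testing is therefore the reading that fits 25.

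**Effect of a systematic shift.** Suppose naloxone has no effect and knowledge of treatment shifts the symptom difference by b points. The treatment estimate then centres on b. Order and period terms do not absorb it, because b follows the treatment in both sequences. The rejection probability is the chance that a noncentral t variable with noncentrality b/SE exceeds the two-sided 5% limits.

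| Assumed b | Share of 7.53 | b/2.58 | False-positive rate, n = 25 | n = 28 (SE 12.9/√28 = 2.44) |
|---|---|---|---|---|
| 0 | 0% | 0 | 5.0% | 5.0% |
| 1 | 13% | 0.39 | 6.6% | 6.8% |
| 2 | 27% | 0.78 | 11.6% | 12.4% |
| 3 | 40% | 1.16 | 20.1% | 22.1% |

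The column for 28 is shown because sections 8.0 and 16.2 also give that number of completers. The values of b are assumptions; the documents give none.

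**The case against.** The strongest case on the other side is that single-blind is a declared choice, stated consistently, in a proof-of-principle trial. A reader might infer three stronger things that the documents do not support.

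- *That the single-blind label conflicts with section 4.2.* It does not. A pharmacy service can hold the list and dispense in a single-blind trial.
- *That staff know the treatment.* No section says that clamp staff receive the assignment, or whether the same people work on both days. The documents support only that staff may know, because nothing prevents it.
- *That the analysis has no answer to any of this.* Section 16.1 plans to compare metabolic conditions between active and saline studies and, if they differ meaningfully, to repeat the treatment comparison with adjustment, separately for epinephrine and symptoms. The parameters are not listed, but this could reduce bias that acts through clamp conduct.

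Other safeguards count too. If participants are masked, the person who reports symptoms is masked, and uses a standard questionnaire at fixed times. Exercise workload is tied to measured VO2, and the clamp has a set insulin rate and glucose level with bedside glucose readings. Epinephrine is a laboratory value. The DSMB reviews early stopping and adverse events.

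These points narrow the concern but do not remove it. Adjustment for metabolic conditions does not reach prompting during the questionnaire. DSMB review does not mask the person who decides to stop or judges causality. And the masking of the participant is itself inferred from usage, and could be weakened by sampling in one period only.

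**Conclusion.** The point holds as an unspecified and cheaply improved safeguard, not as a contradiction or an established bias. The plan does not name the blinded party and masks none of the people who handle the Day 2 outcomes or judge causality. That leaves an avoidable route to bias, mainly for the Aim 1 symptom score and less for epinephrine.

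If participants are the blinded party, the route is indirect: prompting, clamp conduct and early stopping. Its size is unknown. The rise from 5% to about 7% to 20% rests on an assumed shift of 1 to 3 points, the plan's SD of 12.9, 25 completers and a two-sided test. It shows how sensitive the Aim 1 test is and is not evidence that such a shift will occur. Confidence is medium, because the documents are silent on what staff will in practice know. If staff are already masked, most of the remedy is a correction of wording.

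**What to change.** 1. In sections 4.1 and 5.1, state who is blinded, and extend the blind to those who run the Day 2 clamp, collect the questionnaires and judge adverse-event causality.
2. In section 4.2, state that Investigational Drug Services holds the list, issues coded doses and keeps an emergency code-break. The DSMB stays unblinded, and authority to stop a session for safety is untouched.
3. Reconcile section 5.2 with the schedule table on naloxone sampling, so that sampling does not show the treatment. Either draw on the same schedule from the existing IV line in both periods and leave the saline-period samples unassayed, or withhold Day 1 dosing and sampling records from Day 2 staff. Coded sprays alone would not be enough under the schedule's present note. The second option does not hide the sampling from anyone present on Day 1.
4. Say how far the saline device matches the active one. Where the two cannot be made alike, arrange among existing staff that whoever gives the Day 1 spray does not collect the Day 2 questionnaires.

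The sample size, visits and analysis model do not change. The cost is an amendment, some pharmacy labelling and scheduling work, and possibly a few extra tubes in the saline period. How easily existing staff can be split between days cannot be judged from the documents. Masking may remain incomplete for whoever gives the Day 1 spray.

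### Section 5.2 describes the final Day 1 dose as naloxone only, contradicting the naloxone-or-saline wording elsewhere; the timing of the second dose in each session also conflicts

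*Combined protocol and SAP*

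**What the plan says.** Section 5.2 (Part 1 Day 1) sets out two morning and two afternoon administrations.

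- **Doses 1 and 2**, at the start of morning exercise and 45 minutes later: "participants will be given a 4.0 mg doses of intranasal naloxone or saline in the same volume, according to the randomization assignment".
- **Dose 3**, at the start of afternoon exercise: "A third dose of 4.0 mg intranasal naloxone or the same volume of saline will be administered".
- **Dose 4**, in the second half of the dose 3 sentence: "a final dose of 4.0 mg intranasal naloxone will be given 45 minutes after the start of the afternoon exercise".

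Part 2 repeats Part 1 apart from the switch of therapy, so the dose 4 wording carries into both parts.

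The schedule of events (after Section 5.3) has one row for naloxone/saline, marked for the morning and afternoon sessions of both parts. Its footnote 1 reads "Naloxone/saline 4.0mg administered twice, time zero and +30 minutes". The crossover rule in Section 5.2 is "Those who received naloxone in Part 1 will receive saline in Part 2, and vice versa". Section 5.1 gives the purpose as to "compare the impact of intranasal naloxone vs. intranasal saline administration during exercise on day 1". On supply, Section 4.2 states "Investigational Drug Services will handle all drug requirements including randomization and blinding, dispensing, and storage".

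**The concern.** Dose 4 is the only Day 1 administration described without saline. The omission comes straight after a clause that does name saline, so a reader could take the difference as deliberate. The sentence belongs to the current procedures text, from which worksheets and pharmacy instructions may be written.

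Both primary outcomes (Section 3.1) are naloxone-versus-saline differences measured at the Day 2 clamp: symptom scores and peak epinephrine. An active dose in the saline part, and the last one before the clamp, would erode the control condition for both. If it happened in every saline part, it would occur in both treatment orders and both periods. The order and period terms in the Section 16.1 mixed model could not separate it from a smaller treatment effect. The schedule limits naloxone sampling to active drug, so plasma levels would not expose it either.

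**Working it through.** **1. The sources side by side**

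| Source | Content of dose 4 | Time of the second dose in a session |
|---|---|---|
| Section 5.2, doses 1 and 2 | not covered (these doses are naloxone or saline) | 45 minutes after morning start |
| Section 5.2, dose 4 | naloxone only | 45 minutes after afternoon start |
| Schedule row and footnote 1 | naloxone or saline | +30 minutes |
| Crossover rule, Section 5.2 | one therapy per part, the other in the other part | not stated |
| Section 5.1 contrast | naloxone against saline | not stated |

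There are two conflicts. On content, the dose 4 sentence stands alone against the other sources. On timing, Section 5.2 is consistent with itself and footnote 1 differs, for both sessions and both parts. No other text settles the timing.

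**2. Exposure under the literal reading**

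- Naloxone part: 4 doses x 4.0 mg = 16 mg.
- Saline part: 3 saline doses + 1 x 4.0 mg = 4 mg.
- Ratio: 4/16 = 25% of the active exposure, against 0 mg if all four doses are saline.

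**3. The plan's own Aim 1 figure**

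Inputs from Section 16.2: 25 completers, SD of paired differences 12.9, difference 7.53 points, 80% power. Section 16.1 gives a significance level of 0.05; two-sided is assumed, since sidedness is not stated.

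- Noncentrality = (7.53/12.9) x √25 = 0.5837 x 5 = 2.92, with 24 degrees of freedom.
- Paired t-test power = 79.96%. The difference detectable at 80% power is 7.534 points.

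The plan's figure reproduces. The dose 4 wording does not enter this calculation, so correcting it changes no sample-size or power figure.

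**4. Illustration of what literal dosing could cost**

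The documents give no effect for a single dose. Assume that one active dose in the saline part produces a fraction f of the full effect. The remaining difference is then 7.53 x (1 − f), with SD and completers as above.

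| f (assumed) | Remaining difference, points | Power, 25 completers |
|---|---|---|
| 0 | 7.53 | 80% |
| 0.10 | 6.78 | 71% |
| 0.25 | 5.65 | 56% |
| 0.50 | 3.77 | 29% |
| 1 | 0 | 5% |

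The table shows that the question matters. It does not estimate a bias.

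**The case against.** The strongest reply is that nobody reading the whole protocol would give naloxone in a saline part. Participants are randomized to naloxone or saline before any other procedure that day. The crossover rule allows one therapy per part. Footnote 1 covers both doses of each session as naloxone/saline. Restricting naloxone sampling to active drug presupposes a part without it. Investigational Drug Services controls randomization, blinding and dispensing in a single center, so an error would need that service to supply an active unit for a part assigned to saline. On this view two words were left out because saline had just been named in the same sentence.

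Most of that stands. A reader might infer that a site following the protocol would contaminate the placebo condition, or that no participant has an exercise day free of opioid blockade. The documents do not support either inference: both require reading half a sentence against everything else, and nothing shows that a mis-dose was planned or occurred.

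Two things survive the reply. The schedule cannot simply be taken as the tie-breaker, because its footnote disagrees with Section 5.2 on the timing of this same administration. And the pharmacy instructions and dosing worksheets are not in the documents, so whether the wording passed into them cannot be seen from here.

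**Conclusion.** The dosing text is wrong as written: it contradicts itself on the content of dose 4, and it contradicts the schedule on the timing of the second dose in each session. The content conflict is most likely a drafting omission. It still needs correcting, because it concerns what participants receive in the control condition of both primary comparisons.

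If the sentence were followed literally, the saline part would carry 4 mg against 16 mg. Both contrasts would be biased toward no difference, assuming that a single dose acts in the same direction as four. It is tempting to turn the 25% exposure ratio into a 25% loss of effect. That needs a response proportional to dose, and the documents give no dose-response information; Section 1.1 leaves the minimum effective dose to later work. The size of the bias is therefore not estimable, and the power range above rests wholly on the assumed f. The Aim 1 sample size of 25 completers is unaffected.

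**What to change.** Reconcile the dosing paragraphs of Section 5.2 with the schedule row and footnote 1, on both the content and the timing of the second dose in each session. Which statement is right is for the sponsor and investigator to settle. Then check that the pharmacy instructions and dosing worksheets match the reconciled text. For any participant already treated, confirm from dispensing records what was given as dose 4 in each part; plasma samples cannot answer this for the saline part.

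The cost is a short protocol amendment and a review of records, with no added visits, drug or participants. If the records show active drug in any saline part, that should be reported and taken into account when the treatment contrasts are interpreted.
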